6.2.4 ACCOUNTABILITY

MED-EL will be responsible for creating and storing records related to device accountability and traceability. Shipment records, including name and address of the study site, participant ID, device information, date of shipment, and serial numbers, will be stored at MED-EL according to the relevant SOPs. Study devices returned to MED-EL will be documented and stored accordingly.

7 STUDY PROCEDURES AND SCHEDULE

7.1 STUDY PROCEDURES

7.1.1 STUDY SPECIFIC PROCEDURES

The following procedures will be performed during the study and will be documented for each participant enrolled:

- Informed consent: Site study personnel will review the IC form with potential participants and obtain signature prior to initiating study activities. Participants will be allowed to ask questions and may withdraw consent at any time.
- Parental/Legal Guardian permission: Site study personnel will review the parental permission form with the parents/legal guardians and obtain parental permission before starting study activities. Parents/guardians will be allowed to ask questions and may withdraw consent at any time.
- Assent: If required by the IRB, site study personnel will review the assent form with the potential participant and obtain assent before starting study activities. Potential participants will be allowed to ask questions and may withdraw assent at any time.

- Patient-Reported Outcomes:
 - Audio Processor Comparison Survey (APCS): Participants will complete the APCS at Visit 2. The APCS includes questions arranged into four subsections that assess user or parent satisfaction with design, Bluetooth pairing, and backwards compatibility with the SONNET 3 (EAS) compared to the existing audio processor. Responses are captured with a 6-point Likert scale, and responses from the Design subsection will be analyzed for the primary endpoint. Responses on all other subsections will be summarized for the secondary endpoint.
- Audiologist Outcomes:
 - Audiologist Survey: This custom survey assesses clinician impressions of device usability with SONNET 3 (EAS) compared to the existing models, SONNET/SONNET 2 (EAS). The survey features three subsections and responses are captured with a 6-point Likert scale. This survey will be completed by the audiologists upon conclusion of enrollment.

7.1.2 STUDY INTERVALS

- Visit 1: Enrollment/Baseline
- Visit 2: 3-week Interval (2-4 weeks after Visit 1)
- Enrollment Conclusion

Testing can occur outside of the provided window with prior approval from MED-EL.

7.2 STUDY SCHEDULE

7.2.1 POTENTIAL PARTICIPANT IDENTIFICATION

Potential participants will be recruited through the outpatient clinics at a single academic medical center. The site may review existing records for patients to determine potential participants. Participants may also be recruited by their clinical audiologists, who will refer the potential participant to the clinical research team to verify candidacy. Study-related procedures will occur after informed consent or parental permission and assent (if required) forms have been explained and signed. Participants who are suitable candidates for the study should complete the enrollment/baseline procedures in [Section 7.2.2](#).

7.2.2 VISIT 1: ENROLLMENT/BASELINE

- Informed consent
- Parent/Legal Guardian permission (if applicable)
- Assent (if applicable and required by IRB)
- The participant's existing fitting map will be converted for use with SONNET 3 (EAS), keeping all fitting parameters identical to their current fitting MAP

- Participant instructed on use of SONNET 3 (EAS) AP for take-home trial
- Visit 1 case report form (CRF) is completed

7.2.3 VISIT 2: 3-WEEK INTERVAL

- Audio Processor Comparison Survey is completed by subject
- Visit 2 CRF is completed

7.2.4 ENROLLMENT CONCLUSION

- Audiologist Survey is completed

7.2.5 SCHEDULE OF EVENTS TABLE

	Enrollment	Visit 1	Visit 2	Enrollment Conclusion
Informed Consent	X			
Audio Processor Comparison Survey			X	
Study Exit			X	
Audiologist Survey				X

7.3 PRECAUTIONARY PROCEDURES

Not applicable

7.4 PROHIBITED PROCEDURES

Participants should have a stable map before enrolling. The goal is to compare the same fitting map in each process to isolate only characteristics that are new to SONNET 3 (EAS). Unilateral and bilateral study participants will receive one SONNET 3 (EAS) Audio Processor for the take-home trial period and should avoid reprogramming the existing audio processor on either ear between study visits.

8 ASSESSMENT OF SAFETY

8.1 DEFINITIONS AND CLASSIFICATIONS

8.1.1 DEFINITION OF ADVERSE EVENTS (AE)

An adverse event is any unfavorable change in the health of a participant that happens during a clinical study or immediately after the study has ended. This change may or may not be caused by the intervention studied ([Glossary of Common Site Terms - ClinicalTrials.gov](#)).

8.1.2 DEFINITION OF ADVERSE DEVICE EFFECTS (ADE)

Adverse events will be reported as related to the study device if the event is known to occur with audio processor use or programming in the MAESTRO System Software, or if there is a reasonable possibility that the audio processor or programming software caused the event. Reasonable possibility means that there is evidence to suggest a causal relationship between the study device and the event. Events occurring immediately after programming the device or use of the audio processor during the trial may also suggest a device-related adverse event.

8.1.3 DEFINITION OF SERIOUS ADVERSE EVENTS (SAE)

Adverse events are considered serious when they result in death or any injury or illness that is life-threatening, results in permanent impairment or damage to the body, or requires medical or surgical intervention to prevent permanent harm to the body.

8.1.4 DEFINITION OF UNANTICIPATED ADVERSE DEVICE EFFECTS (UADE)

Unanticipated adverse device effects are defined as any event not previously known to occur with audio processor or software use. Risks associated with the device are detailed in Section 2.3.1 above. Events can be unexpected in nature, severity, or degree of incidence. This definition could include an unanticipated adverse device effect or other serious adverse effect associated with the device, if the problem was not previously identified in nature, severity, or degree of incidence.

[figure not shown]
8.2 TIME PERIOD AND FREQUENCY FOR EVENT ASSESSMENT AND FOLLOW-UP

The occurrence of an adverse event may be brought to the attention of investigators during study visits, interim visits, or phone calls during the study. All adverse device effects will be recorded on the Adverse Event Report Form (CRF), including event description, date of onset, time of onset, relationship to the device, seriousness, unexpectedness, and the date/time of resolution (if applicable). Adverse events will continue to be followed until reaching adequate resolution or stabilization. Additional information for an ongoing adverse event will be reported as part of the same event and will not constitute a new event.

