2.3 RISK/BENEFIT ASSESSMENT

2.3.1 KNOWN POTENTIAL RISKS

Any cochlear implant processor poses a risk of skin irritation or sensitivity to the processor materials. Materials in the SONNET 3 (EAS) (EAS) Audio Processor do not differ from those in the FDA-approved SONNET/SONNET 2 (EAS) Audio Processors. MED-EL has performed biological safety and compatibility testing with materials in the SONNET 3 (EAS) (EAS), and subjects with a skin or scalp condition that would preclude use of the audio processor will be excluded from this study. All cochlear implant processors and fitting software also pose a risk of overstimulation

and exposure to unwanted or uncomfortable sounds. The processor can be removed from the head at any time to immediately stop stimulation.

There is a remote chance that technical failure or suboptimal fitting of any audio processor leads to unwanted sensations, missing information, suboptimal hearing, or lack of benefit. Study participants who wish to stop using the SONNET 3 (EAS) (EAS) Audio Processor before study completion may withdraw from the study at any time and continue using their existing audio processor. Participants who experience poorer sound quality or performance with SONNET 3 (EAS) (EAS) may be reprogrammed after testing at Visit 2.

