2.2.3 ASSESSMENT OF KNOWN POTENTIAL RISKS AND BENEFITS

This study will include experienced MED-EL CI users who have worn an FDA-approved SONNET (EAS) or SONNET 2 (EAS) Audio Processor (P000025/S078 and P000025/S112, respectively) for at least 12 months. The SONNET/SONNET 2 (EAS) Audio Processors (AP) are part of the MED-EL Cochlear Implant System (P000025). The SONNET 3 (EAS) (EAS) AP is not expected to pose any greater risk of harm to participants than SONNET/SONNET 2 (EAS) APs. Advances in technology with SONNET 3 (EAS) (EAS) may provide new design features to improve wearing comfort and streamlined connectivity to improve usability. Thus, the benefits of SONNET 3 (EAS) (EAS) are expected to outweigh the residual risk in this population. Periodic advances in audio processor technology are standard practice and expected in the field of cochlear implants. This study is intended to collect clinical data on patient-reported satisfaction and performance with SONNET 3 (EAS) (EAS) before commercial availability in the United States to assist with future product launch and insurance coverage.

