8.3 REPORTING PROCEDURES

8.3.1 ADVERSE EVENT REPORTING

Any adverse device effect discovered during the study should be recorded on the Adverse Event CRF by an investigator and reported to MED-EL. Investigators are responsible for determining if the adverse event meets the definitions for device -related, serious, and/or unanticipated. Questions regarding classification should be directed to the MED-EL Clinical Monitor. All ADEs should be reported to the MED-EL Clinical Monitor in a timely manner. All adverse device effects will be reported to the FDA and to relevant IRBs in the annual report. Investigators should reference the flow chart below (Figure 1) and Section 8.3.2 to determine appropriate reporting procedures, depending on AE type.

(FIGURE 2)

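### The protocol describes passive adverse event ascertainment and lists no visit procedure that asks about events, so mild device effects in the take-home trial may be under-recorded

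*Combined protocol and SAP*

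**What the plan says.** Section 8.2 is the protocol's statement on how and when events are assessed. It reads: "The occurrence of an adverse event may be brought to the attention of investigators during study visits, interim visits, or phone calls during the study". It gives no frequency and nobody a duty to ask. Section 8.3.1 also waits for an event to surface: "Any adverse device effect discovered during the study should be recorded on the Adverse Event CRF by an investigator".

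The visit lists add nothing active:

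- **Visit 1 (7.2.2):** consent, permission and assent, map conversion, instruction on use, and a Visit 1 case report form.
- **Visit 2 (7.2.3):** "Audio Processor Comparison Survey is completed by subject", and a Visit 2 case report form. This is the only scheduled participant contact after fitting, and 7.2.5 marks it as study exit.
- **Schedule of events (7.2.5):** four rows, namely informed consent, the Audio Processor Comparison Survey (APCS), study exit and the Audiologist Survey.

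Section 8.2 mentions interim visits and phone calls, but 7.1.2 and 7.2.5 schedule none.

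On risk, 2.3.1 states: "Any cochlear implant processor poses a risk of skin irritation or sensitivity to the processor materials". It also names overstimulation, uncomfortable sounds, unwanted sensations and technical failure. Section 2.2.3 says that the new processor "is not expected to pose any greater risk of harm to participants than SONNET/SONNET 2 (EAS) APs". Section 10.4.4 marks safety analyses as not applicable.

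**The concern.** The risks in 2.3.1 are mostly of a kind that people may not volunteer. Section 2.3.1 notes that stimulation stops at once when the processor is taken off, so an episode of uncomfortable sound in the first days at home may be long over, and not thought worth mentioning, by Visit 2. Minors may take part (5.3), and their events may reach the site only through a parent.

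Participants who leave early are the easiest to miss. Under 5.4.2 they may be replaced and no further data are collected from them, so someone who stops because of a device effect might leave no record of it.

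Three parts of the protocol depend on what is recorded:

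- the annual report of all adverse device effects to the FDA and IRBs (8.3.1);
- the definition in 8.1.4, under which an effect can be unanticipated by its degree of incidence;
- the example in 8.4 of a rise in event frequency as a trigger for safety review.

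If an unknown share of mild events is missed, each works from an incomplete count.

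**Working it through.** The protocol gives no expected event rate, safety sample size or safety power, so there is no stated figure to reproduce. The check is first textual, then a short illustration of scale.

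**Step 1. Set the named risks against the listed procedures.**

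| Risk in 2.3.1 | Asked about in 7.2.2, 7.2.3 or 7.2.5? |
|---|---|
| Skin irritation or sensitivity | No |
| Overstimulation, uncomfortable sound | No |
| Technical failure, unwanted sensations | No |

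The only participant questionnaire is the APCS. Sections 3 and 7.1.1 describe it as covering satisfaction with design, Bluetooth pairing and backwards compatibility, plus parent impressions. It is not presented as a safety instrument. Nothing in sections 8 or 10 supplies active collection.

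**Step 2. What an empty event log could mean.** Inputs: n = 20 (4.1); zero recorded events (hypothetical); s = the share of affected participants whose event is recorded. The documents do not give s, so it is varied from 100% to 25%.

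Exact one-sided 95% upper bound on the recorded rate for 0 of 20:

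1 − 0.05^(1/20) = 0.139, or 13.9%.

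If a true rate p is recorded at rate p × s, the bound on p is 0.139 / s:

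| s (assumed) | Upper bound on true rate |
|---|---|
| 100% | 13.9% |
| 75% | 18.5% |
| 50% | 27.8% |
| 25% | 55.6% |

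**Step 3. Chance of an empty log at a given true risk.** P(no event recorded) = (1 − p × s)^20.

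| True risk p | s = 100% | s = 75% | s = 50% | s = 25% |
|---|---|---|---|---|
| 10% | 12% | 21% | 36% | 60% |
| 20% | 1% | 4% | 12% | 36% |

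For example, at p = 10% and s = 50%: (1 − 0.05)^20 = 0.358. At a true risk of 10%, halving capture raises the chance of an empty log from about one in eight to more than one in three.

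**Step 4. What better capture can and cannot do.** At s = 100% the bound is still 13.9%, and the study collects no event rate on the existing processors. Asking makes the count interpretable. It does not make it a comparison.

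**The case against.** The strongest reply is that a reader cannot know that nobody asks. The contents of the Visit 2 case report form, the adverse event form and the reporting flow chart are not shown, and one of them may hold a question. The missing schedule row is weak evidence by itself, because 7.2.5 also omits device fitting, map conversion, instruction and both visit forms, all of which 7.2 requires. This stands. The point is therefore limited to what the protocol text states. Section 8.2 and the visit lists are still where the requirement belongs.

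A reader might infer that the trial means to show no greater risk from its event count. The documents do not support that. Section 2.2.3 states a prior expectation; 2.3.1 backs it with unchanged materials and completed biological safety testing; section 3 has no safety objective; and 10.4.4 plans no analysis.

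A reader might also infer that the stopping rule in 8.4 is undermined. It counts serious, unanticipated device effects, and the mild events at issue would not enter it. Only the broader frequency example in 8.4 is affected.

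Nor do the documents show that participants would hide events to keep the device. Keeping it is offered after Visit 2 (2.3.2, 6.2.1) with no link to event reports. Section 2.3.1 allows reprogramming after Visit 2 testing when sound is poorer, so some complaints should surface there. Finally, its remark about removing the processor concerns stimulation, and it does not say that removal resolves skin irritation.

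**Conclusion.** The concern holds in limited form. The protocol describes passive ascertainment, and no listed procedure or schedule row asks about events that it names as risks. Mild events may therefore be under-recorded, which weakens the device-effect counts reported under 8.3.1 and the judgements of incidence and frequency in 8.1.4 and 8.4.

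The size cannot be fixed from the documents. The bounds of 13.9% to 55.6% rest on an assumed capture share between 100% and 25%, on capture being independent between participants, and on a hypothetical count of zero. They show direction and scale and do not estimate the shortfall.

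No planned test is affected, and the primary endpoint is untouched. The limit on any statement about relative safety comes from 20 participants, 2-4 weeks of exposure and the absence of a comparator rate. Better ascertainment would not remove that limit. The change is still worth making because it costs little and the counts go to regulators.

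**What to change.** - **Section 8.2:** state that participants or parents will be asked about adverse events at Visit 2 and at any withdrawal contact, in addition to events that come to light in other ways.
- **Sections 7.2.3 and 7.2.5 and the Visit 2 case report form:** add an adverse event entry at Visit 2. Use one non-leading open question, then yes/no items for the risks in 2.3.1 (skin irritation or sensitivity; overstimulation or uncomfortable sound; technical failure). If the form already has such a question, cite it in the protocol.
- **Order:** ask after the APCS is completed. Questions about soreness or discomfort put first could lower the Design ratings, which are the sole primary endpoint (10.4.2).
- **Section 5.4.2:** amend the bar on further data from withdrawn participants so that the same questions can be put at withdrawal contact.

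The cost is a few minutes at an existing visit, a few lines on a form, and a higher recorded count of minor events, which should be expected when the results are read. No visit is added.

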8.4 STUDY HALTING RULES

MED-EL will review all serious, unanticipated adverse device effects to determine if the study should continue per the protocol, be modified, or be discontinued. Examples of findings that would trigger a safety review are the number of serious adverse events occurring overall, the number of occurrences of a particular type of serious adverse event, or increased frequency of events (e.g., device deficiencies). If findings indicate that the study or protocol should be reconsidered, MED-EL will inform FDA of the disposition of the study.

A stopping rule of three unanticipated serious adverse device effects would prompt suspension of enrollment and/or study intervention use. Based on the definitions of an Adverse Device Effect, Serious Adverse Event, and Unanticipated Adverse Event provided in Sections 8.1.2, 8.1.3, and 8.1.4, respectively, a Serious unanticipated Serious Adverse Device Effect:

1. Results in death, injury, or illness that is life-threatening; results in permanent impairment or damage to the body; or requires medical or surgical intervention to prevent death, life-threatening injury/illness, or permanent harm to the body,
2. Is unanticipated in nature, severity, or frequency from the known potential risks,
3. Is related or possibly related to participation in the research,
4. Suggests that the research places participants or others at a greater risk of harm than was previously known or recognized, and
5. There is a reasonable possibility that the device caused the event

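### Sections 8.2 and 8.3.1 require capture of adverse device effects only, so the wider serious-event and device-deficiency counts that Section 8.4 lists as safety-review triggers would be incomplete

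*Combined protocol and SAP*

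**What the plan says.** Section 8.1.1 defines an adverse event without regard to cause: "This change may or may not be caused by the intervention studied". Section 8.1.3 defines seriousness by outcome alone and sets no condition of relatedness.

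The two sentences that create the duty to record are narrower. Section 8.2: "All adverse device effects will be recorded on the Adverse Event Report Form (CRF"). Section 8.3.1: "Any adverse device effect discovered during the study should be recorded on the Adverse Event CRF by an investigator and reported to MED-EL". Expedited reporting in Section 8.3.2 is narrower again, covering events that are at once unanticipated, serious and device-related.

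Section 8.4 then gives examples of findings that would trigger a safety review. The first is "the number of serious adverse events occurring overall". The others are the count of one kind of serious event and an increased frequency of events, with device deficiencies as the illustration. The same section has the sponsor review serious, unanticipated device effects to decide whether the study continues, and it sets a suspension threshold of three such effects.

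**The concern.** An overall count of serious events needs every serious event as input, but the recording duty admits only those already classed as device effects. That classing is done at the site: "Investigators are responsible for determining if the adverse event meets the definitions for" device-related, serious and unanticipated events. The study is open-label (Section 4.1), so the person making the call knows which device is worn.

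At stake is the sponsor's ability to see a pattern across participants. Section 8.1.4 accepts that an effect may be unexpected in how often it occurs, and that can be judged only by counting. For an event not already known to occur with the processor, Section 8.1.2 asks for evidence of a causal link, and a new kind of event may offer none on first appearance. If such events are screened out one by one before recording, the count meant to reveal the pattern leaves them out.

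**Working it through.** There is no figure in the plan to reproduce. The check compares the provisions and then sizes the gap.

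**Which events the visible text requires to be captured**

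| Event | Recorded and reported under 8.2 and 8.3.1? | Needed for a Section 8.4 provision? |
|---|---|---|
| Serious, unanticipated, device-related | Yes, and expedited under 8.3.2 | Yes: continuation review, three-event threshold, serious-event counts |
| Serious, anticipated, device-related | Yes | Yes: serious-event counts |
| Serious, judged unrelated | No visible requirement | Yes: serious-event counts |
| Device deficiency without an adverse device effect | No visible requirement | Yes: event-frequency example |
| Non-serious, judged unrelated | No visible requirement | Not named there |

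The first row supplies everything the continuation review and the suspension threshold use. The third and fourth rows are the gap. The overall serious-event count, followed literally, becomes the count of serious device effects.

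**How many serious events could be involved**

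Inputs: 20 participants (Section 5.3) and about 1 month of participation each (Section 1.1). The documents give no background rate of serious events, so an all-cause rate of 0.05 to 0.20 per person-year is assumed.

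- Exposure: 20 × 1/12 = 1.67 person-years.
- Expected serious events, rate × exposure: 0.05 × 1.67 = 0.08; 0.20 × 1.67 = 0.33.
- Poisson chance of at least one, 1 − exp(−m): 1 − exp(−0.083) = 8%; 1 − exp(−0.333) = 28%.
- Poisson chance of at least two, 1 − exp(−m)(1 + m): 0.3% at m = 0.083; 4.5% at m = 0.333.

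These are all-cause figures. Events judged unrelated are a subset, so the number omitted can be no larger.

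**The case against.** The strongest reply is that the protocol uses two terms loosely and intends wider capture. The form is named for adverse events, and its fields include "relationship to the device, seriousness, unexpectedness, and the date/time of resolution (if applicable"); a relationship field adds little if every entry is already device-related. Section 8.1.2 reads as if classification follows reporting: "Adverse events will be reported as related to the study device if the event is known to occur with audio processor use". Section 8.2 says that adverse events will be followed to resolution. Section 8.3.1 adds: "Investigators should reference the flow chart below (Figure 1) and Section 8.3.2 to determine appropriate reporting procedures, depending on AE type". That chart is not visible here and may cover unrelated serious events.

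Much of this stands as evidence of intent, but it does not supply the missing duty. The sentence holding the relationship field is itself about device effects, and follow-up at the site is not reporting to the sponsor. If the chart does require unrelated serious events to be reported, it is wider than the two written sentences, and they should be brought into line with it.

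Monitoring also gives partial cover. Monitors have access to source records (Section 11) and compare study records with source (Section 12), and terminations, including those for health concerns, are reported to them (Section 5.4.1). A reader might infer that an unrelated serious event could never reach the sponsor; these provisions show otherwise. They are still no substitute for a defined report, because the completeness review in Section 9 looks at completed records and would not flag an event for which no entry was required.

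Finally, the overall count is one of several examples in Section 8.4 and has no threshold attached. That is correct, and it limits the weight of the point.

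**Conclusion.** The mismatch is real and narrow. On the visible text, the serious-event counts in Section 8.4 would omit serious events judged unrelated, and the frequency of device deficiencies has no stated recording duty behind it. The practical size is small: fewer than one serious event of any cause is expected under the assumed rates, and two or more have at most about a 4.5% chance. No efficacy result is touched.

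Three stronger readings are tempting and are not supported:

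- That the overall-count trigger has no data. Serious device effects are recorded with a seriousness field, so the count is incomplete, not empty.
- That the safety review or stopping rule cannot operate. The continuation review and the three-event threshold both use events that Sections 8.2 to 8.3.2 require to be recorded and reported.
- That every non-serious adverse event must be captured. The Section 8.4 provisions at issue concern serious events and device deficiencies, so the mismatch does not extend that far.

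The conclusion depends on the visible text. If the flow chart already covers unrelated serious events, what remains is an inconsistency between the chart and the two sentences.

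**What to change.** Reconcile Sections 8.2 and 8.3.1 and the flow chart with Section 8.4. State in both recording sentences that, in addition to adverse device effects, all serious adverse events and all device deficiencies are recorded on the Adverse Event CRF and reported to the sponsor, regardless of the investigator's judgement of relationship to the device. Keep the relationship, seriousness and unexpectedness fields, so that device effects are identified from the recorded events. Section 8.3.2 and the suspension threshold stay unchanged.

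The contradiction could also be removed by cutting the Section 8.4 examples back to device effects. That would make the text consistent but would give up the overall view of serious events that the protocol says it wants.

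The cost is a wording change in two sections, a check of the flow chart, and a few extra forms at most. With about 1.67 person-years of exposure, few additional serious-event reports are expected. The documents give no basis for a rate of device deficiencies, so the number of those forms cannot be estimated.
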